4.3 Subject Withdrawal

A subject may withdraw from the study at any time and for any reason without prejudice to their future medical care by the Investigator or at the clinical study site.

Withdrawal from the study will occur under the following circumstances:

- Death
- Withdrawal of consent
- Lost to follow-up
- Study termination by Sponsor

If a subject is lost to follow-up, a minimum of two attempts should be made by the study site personnel to contact the subject. Appropriate contact includes 2 documented phone calls followed by a registered letter before a subject may be listed as lost to follow-up. The measures taken for follow-up and reason for premature study discontinuation should be documented in source documents and CRF.

When a subject withdraws from the study, the reason(s) for withdrawal are to be recorded on the CRF. Whenever possible, all subjects who withdraw from the study are to be encouraged to undergo the End-of-Study assessments at the time of withdrawal.

Sites should obtain follow-up data on any subject who withdraws from the study and has ongoing AEs of interest or SAEs related to ADVM-043. In every case, efforts must be made to undertake protocol-specified safety follow-up procedures.

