6.8 Serious Adverse Event Reporting

SAEs related to ADVM-043 should be recorded on the CRF by the Investigator or designee (Section 6.3). The Investigator must report a related SAE to the Sponsor within 24 hours of awareness of the event to meet regulatory and patient safety obligations. For additional details on reporting of safety reports please refer to the Investigator Study Manual.

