6.10 Request for Autopsy in the Event of a Subject Death

In the event of a subject death while participating in the study, the Investigator should request a full autopsy to determine the precise cause of death. If possible, samples of tissues obtained at autopsy should be evaluated for the presence of the AAV genome.

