8.0 STATISTICAL PLAN

Descriptive and exploratory analyses are to be performed on all data to gain insight into the safety of ADVM-043. Adverse event data are to be analyzed overall, by dose level administered, and by study. Refer to the Statistical Analysis Plan.

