7.2 Secondary Endpoints

Not applicable

8 Statistical Methods

All analyses will be done using SAS (version 9.4, [REDACTED]).

Safety endpoints will be analyzed in a descriptive manner. Continuous data will be reported using the following descriptive statistics:

1. Number of observations (n)
2. Mean and Standard deviation (SD)
3. Median
4. Minimum (min) and Maximum (max)

Minimum and maximum values will be reported in the units of collection with 3 decimals being maximum value; the mean will be presented with 1 decimal place more and the standard deviation 2 decimal places more than the units of collection. Categorical data will be presented using frequency (n = number of subjects; m = number of events) and percentage (%).

Listings will be provided for all data recorded in eCRF to study subject profiles. All listings will be sorted by cohort, subject ID, and date (if applicable). Unscheduled visit data will only be listed and not included in summaries.

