10.6 Adverse Events Flags

An AE is any untoward medical occurrence in an enrolled subject, regardless of its causal relationship to the investigational medicinal product.

Only AEs of interest will be collected and reported in the current study. AEs of interest that are continuing from the previous study will be imported for long term follow-up.

AEs of interest include:

- new malignancy
- new incidence or exacerbation of a pre-existing neurologic disorder
- new incidence or exacerbation of a prior rheumatologic or other autoimmune disorder
- unexpected hospitalization

Study Period:

All AEs will be counted once under the below period in which the AE has started.

- Previous Study: Reported from AE (External).
- Screening – Year 1: If AE start date is after screening and on or before Year 1 visit date.
- Year 1 – Year 2: If AE start date is after Year 1 and on or before Year 2 visit date.
- Year 2 – Year 3 (EOS): If AE start date is after Year 2 and on or before Year 3 visit date.

Related Adverse Events:

- AE (External): includes Possibly, Probably and Definitely Related Adverse Events
- AE: includes Definitely and Likely Related Adverse Events.

Relationship to ADVM-043 will be flagged separately.

Severity:

Subjects with the same AE of interest and different severities will be flagged for the most intense severity. i.e., If the same event has been reported twice with severity 'Grade 1 – Mild' and 'Grade 3 – Severe' then the subject will be flagged as 'Grade 3 – Severe'. AEs that are missing severity will be presented in summary tables as 'Grade 3 – Severe'.

Duration of AEs:

Duration of Adverse events (days) will be calculated as follows: (AE End date – AE Start date) + 1.

For adverse events that are ongoing at end of study, date of end of study will be considered as AE End date.

11 Statistical Analyses

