11.7 Safety Analyses

The long-term safety of ADVM-043 is to be assessed by determining the type, frequency and percentages, severity, duration, and relationship to ADVM-043 of adverse events (AEs) of interest and serious adverse events (SAEs) related to ADVM-043. All safety data will be listed and summarized by cohort using the FAS population.

Only AEs of interest will be summarized.

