11.7.1.3 Summary of Adverse Events by Severity

Number and percentage of subjects in each system organ class, preferred term, and intensity (Grade 1-5) will be summarized by severity for adverse events of interest and cohort. System organ class and preferred term will be displayed by descending order of frequency in “Total”.

12 Changes to Planned Analyses

No changes from the analysis defined in protocol.

13 Index of Tables, Listings and Graphs

Refer [REDACTED] for the list of Tables, Listings and Graphs.

14 References

Provide list of references used to create this document.

- ICH. ICH Harmonized Tripartite Guideline: Statistical Principles for Clinical Trials E9. 1998.
- ASA. Ethical Guidelines for Statistical Practice. Prepared by the Committee on Professional Ethics. 1999.
- ICH. ICH Harmonized Tripartite Guideline: Structure and Content of Clinical Study Reports E3. 1995.

15 Appendices

Not Applicable

16 Change Log

Version	Authored by	Change Date	Change Details	Reviewed by	Review Date
1.0	[REDACTED]	[REDACTED]	First Draft	[REDACTED]	[REDACTED]

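### SAP 8 and SAP 11.7 conflict on AEs recorded at a contact coded as an unscheduled visit; separately, SAP 10.6 leaves some AEs without a study period (minor)

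*SAP*

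**What the plan says.** **Summary rule.** SAP section 8 (Statistical Methods) ends with a general rule: "Unscheduled visit data will only be listed and not included in summaries". It lists no exception, and the SAP does not say what makes a visit unscheduled. For the primary endpoint, SAP 11.7 says "All safety data will be listed and summarized by cohort using the FAS population". It then narrows the summaries to AEs of interest, and 11.7.1.2 adds related SAEs. Protocol 8.0 says "Descriptive and exploratory analyses are to be performed on all data to gain insight into the safety of ADVM-043", and SAP section 12 declares "No changes from the analysis defined in protocol".

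**How events become known.** Assessments may be telephone calls (Protocol 5.0; SAP 5, footnote a). Between visits, Protocol 6.8 applies: "The Investigator must report a related SAE to the Sponsor within 24 hours of awareness of the event". After withdrawal, footnote c of the schedule plans an End-of-Study (EOS) assessment, which Protocol 4.3 encourages but does not require. SAP 10.3 names Early Termination as an analysis visit distinct from Year 3 (EOS).

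**Period rule.** SAP 10.6 places every AE once, by start date, in one of four periods. The last is defined by "If AE start date is after Year 2 and on or before Year 3 visit date". The two earlier on-study periods close in the same way at the Year 1 and Year 2 visit dates. SAP 8.1 rules out imputation of missing data.

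**The concern.** The primary endpoint is the type, frequency, severity, duration and relatedness of AEs of interest and related SAEs. If one rule sends an event to a listing and another sends it to a table, two analysts working from the same database could report different counts. Which count appears would depend on how a site or data manager coded a telephone call.

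The fatal AE row in SAP 11.7.1.1 is the most exposed, because no scheduled assessment of a subject can follow death. The period flag is a lesser matter. It promises that every AE is counted once, but its boundaries cannot deliver that for subjects who leave early or miss a visit.

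**Working it through.** The plan has no figure to reproduce: SAP 4.2 gives no sample size, and no dropout or event rate is stated.

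**1. What the SAP 8 sentence can act on.** Three schedule rows continue after Screening: other investigational therapies, AEs/related SAEs, and concomitant medications. SAP 11 describes a summary for two of them (11.5 for medications, 11.7 for AEs). Visit attendance (11.2) is the only other output the sentence could plausibly affect. Its main targets are therefore AEs and medications.

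**2. Readings for an AE with no later planned assessment.**

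| Contact coded as unscheduled visit? | AEs treated as exempt from SAP 8? | In 11.7.1 tables? |
|---|---|---|
| Yes | No | No, listing only |
| Yes | Yes | Yes |
| No | Either | Yes |

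Only the first row loses the event. Nothing in the SAP says which row applies.

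**3. Size of one loss.** If the subject has no other AE in that table row, the cohort numerator falls by 1 and the percentage by 100/n points. The cohort sizes n are assumed:

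- n = 2: 100/2 = 50.0 points
- n = 3: 100/3 = 33.3 points
- n = 6: 100/6 = 16.7 points
- n = 10: 100/10 = 10.0 points

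**4. Period flag, SAP 10.6 applied literally with no imputation.** Times are illustrative years post-treatment: Screening 0.9 and annual visits at 1, 2 and 3.

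| Pattern | Period |
|---|---|
| All visits held, onset 1.5 | Year 1 – Year 2 |
| Last visit Year 1, onset 0.95, learned later | Screening – Year 1 |
| Last visit Year 2, onset 1.5, learned later | Year 1 – Year 2 |
| Last visit Year 2, onset 2.5, exit assessment at 2.6 mapped to Year 3 (EOS) | Year 2 – Year 3 |
| Exit before Year 1, onset 0.95 | None |
| Last visit Year 1, onset 1.5, no exit assessment | None |
| Last visit Year 2, onset 2.5, no exit assessment | None |
| Last visit Year 2, onset 2.5, exit assessment at 2.6 kept as Early Termination | None |
| Last visit Year 1, onset 1.5, exit assessment at 1.6 mapped to Year 3 (EOS) | None (no Year 2 date) |
| Year 2 missed, Year 3 held, onset 1.5 | None |
| Year 2 missed, Year 3 held, onset 2.5 | None |
| Onset on the screening date | None |
| Onset 3.05, after the Year 3 visit | None |

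Now take exit in each of the two intervals after Year 1, with earlier visits attended and onset after the last of them. The AE is unassigned in 2 of 2 intervals without an exit assessment, 2 of 2 if that assessment is kept as Early Termination, and 1 of 2 if it is mapped to Year 3 (EOS). These are cases, not rates.

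**The case against.** The strongest reply is that SAP 8 speaks of visit data, and a 24-hour SAE report or a notice of death is not a visit. The SAP otherwise handles AEs by event: 10.6 uses the start date, 11.7.1.1 counts the AEs of interest that were reported, and it includes a fatal row. Specific AE rules would normally override a general sentence, and that sentence fits the attendance table in 11.2. Much of this stands, and it rules out several stronger readings that a reader might infer:

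- **That every AE learned outside the schedule is list-only.** This holds only if the contact is coded as an unscheduled visit, and no passage prescribes that.
- **That early exit in general is affected.** An EOS assessment after withdrawal is planned by footnote c, and Early Termination is a named visit, so AEs recorded there are not at issue under SAP 8.
- **That the protocol sets out several routes for new events after exit.** Protocol 4.3 says "Sites should obtain follow-up data on any subject who withdraws from the study", but the sentence goes on to limit this to subjects with ongoing AEs of interest or related SAEs. Protocol 6.10, which opens "In the event of a subject death while participating in the study", asks for an autopsy and sets up no reporting route. Protocol 6.8 is the clear between-visit route, and it covers related SAEs only.
- **That the missing period removes AEs from the primary tables.** No summary described in 11.7.1.1 to 11.7.1.3 is by period, and the table index is redacted, so a by-period output can be neither confirmed nor excluded.

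The reply does not remove the conflict itself. The SAP neither exempts AEs nor defines unscheduled, a telephone call can be an assessment, and the sentence has little to act on besides AEs and medications.

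**Conclusion.** The concern holds within limits. SAP 8 and SAP 11.7 are unreconciled for AEs recorded at a contact coded as an unscheduled visit, and under that coding a literal SAP 8 takes them out of the primary-endpoint tables. The events exposed are those with no later scheduled, EOS or Early Termination assessment, chiefly related SAEs reported between visits and deaths. The effect is 100/n points per affected subject; the 50.0 to 10.0 point range rests wholly on assumed cohort sizes and is not a forecast. How often this would happen cannot be estimated from the documents.

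The period gap in SAP 10.6 is certain on the text but minor. It affects AEs that start after the last attended visit, in an interval bounded by a missed visit, on the screening date, or after the Year 3 visit. For onset after the last attended annual visit, the exception is a subject who attended Year 2 and whose exit assessment is mapped to Year 3 (EOS).

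The first part should be settled before database lock because it touches the primary endpoint; the second can be tidied in the same revision.

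**What to change.** 1. **SAP 8.** Add: *This rule does not apply to adverse events or concomitant medications; every recorded AE of interest, related SAE and recorded medication enters the 11.5 and 11.7 summaries, whatever visit or contact it was recorded at.*
2. **SAP 10.6.** Close the last open period at the study exit date, taken as the latest available of EOS, Early Termination, death or last contact. For a missed visit, use the nominal post-dosing anniversary as the boundary, or the Screening date if later. Assign onset on the screening date to Screening – Year 1 unless the event is imported from AE (External), and assign any recorded onset after the Year 3 visit to the last period. State in SAP 8.1 that these boundaries are a derivation rule and not imputation of missing data.
3. **SAP 10.3 and 11.2.** State whether an EOS assessment after withdrawal is Early Termination or Year 3 (EOS), and show it in the attendance summary.

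The cost is a few sentences of SAP text and some derivation code before database lock, with no new assessments. The documents do not specify a last-contact date on the CRF, which is why the exit date uses the latest date available.

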6.5 Assessment of Causality

The Investigator's assessment of relationship of an AE to ADVM-043 is part of the documentation process, but it is not a factor in determining what is or is not reported. If there is any doubt as to whether a clinical observation is an AE, the event is to be reported.

Investigator should assess potential causes of each AE and events should be considered related if there is “a reasonable possibility of a causal relationship” rather than if “a causal relationship cannot be ruled out.” When assessing causality, Investigators should assess biological balancing — the probability that the suspect drug caused the AE must be weighed against the probability that an alternative candidate caused it.

Causality of AEs should be assessed in relation to ADVM-043, and not prior concomitant medications or study procedures in the previous treatment study. The relationship or association of ADVM-043 in causing or contributing to the AE is to be characterized using the following criteria:

- Definitely Related: A definite causal relationship exists between study drug administration and the AE; including a plausible time relationship to study drug administration, and it cannot be explained by underlying or concurrent disease or other drugs/exposures.
- Likely Related: There is a reasonable possibility that the study drug caused the AE; the event is unlikely attributed to underlying or concurrent disease or other drugs/exposures (i.e., alternative explanation). There is a reasonable time sequence to administration of the study drug.
- Unlikely Related: Underlying or concurrent disease or other drugs/exposures provide plausible alternative explanations. Temporal relationship to study drug administration makes a causal relationship improbable.
- Not Related: There is no association between the study drug and the reported event; there is a clear alternative explanation; a causal relationship is non-plausible.

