11.7.1.1 Overall Adverse Events

Number and percentage of subjects will be summarized by cohort for the following categories:

1. All adverse events of interest reported
2. ADVM-043 related adverse events
3. Adverse events \geq grade 3
4. Serious adverse events
5. ADVM-043 related serious adverse events
6. Fatal adverse events

Percentages will be based on FAS population.

All adverse events will be listed by subject and system organ class. Adverse events will be grouped by subject. Duration of AEs will also be included in the listing.

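### Related AEs are counted on two unmapped causality scales, and the planned summaries do not separate imported events from new ones

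*SAP*

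**What the plan says.** SAP 10.6 defines the related flag once for each of two data sources. For events brought over from the treatment study it states "AE (External): includes Possibly, Probably and Definitely Related Adverse Events". For events recorded in the follow-up study it states "AE: includes Definitely and Likely Related Adverse Events". The same section says what is brought over: "AEs of interest that are continuing from the previous study will be imported for long term follow-up". These events get their own onset period, ahead of the three periods of the follow-up study.

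Protocol 6.5 gives the causality scale for this study: Definitely, Likely, Unlikely and Not Related. Its general instruction is to call an event related when there is "a reasonable possibility of a causal relationship". It sets aside the looser test that causation merely cannot be excluded.

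SAP 11.7.1.1 lists six rows for the overall AE table, shown by cohort. One is "ADVM-043 related adverse events" and another is its serious counterpart. SAP 11.7.1.2 repeats the SOC and preferred-term table for related AEs of interest and for related serious AEs. Neither section splits these summaries by source of the event. The SAP gives no conversion between the scales and plans no sensitivity count.

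**The concern.** Relationship to ADVM-043 is a named component of the primary endpoint (Protocol 2.2.1, SAP 7.1). The study is descriptive and tests no hypothesis, so the summary rows are themselves the result. If one row adds events judged on the treatment study's scale to events judged on this study's scale, a reader cannot tell what degree of suspicion an event needed in order to count. The same word, related, would carry two definitions within one percentage, and nothing in the described tables would show it.

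**Working it through.** The plan states no figure on this point, so there is none to reproduce. The check sets the texts side by side.

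**1. Which categories count as related**

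| | Imported events (SAP 10.6) | Events in this study (SAP 10.6, Protocol 6.5) |
|---|---|---|
| Counted as related | Definitely, Probably, Possibly | Definitely, Likely |
| Not counted | Not stated | Unlikely, Not Related |
| Definitions given in the documents | No | Yes |

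**2. Where the cut falls in this study**

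The lowest category that counts is defined as "Likely Related: There is a reasonable possibility that the study drug caused the AE; the event is unlikely attributed to underlying or concurrent disease", with a reasonable time sequence also required. The next category down begins "Unlikely Related: Underlying or concurrent disease or other drugs/exposures provide plausible alternative explanations" and adds that the timing makes a causal link improbable.

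Take an event with reasonable timing and also a plausible alternative cause. It does not cleanly meet Likely, because the alternative is not unlikely. It does not cleanly meet Unlikely, because the timing is not improbable. The general instruction in Protocol 6.5 asks the investigator to weigh the two explanations, so the event could be placed on either side of the cut.

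**3. How this compares with Possibly**

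Three cases are open:
- Likely takes in everything the treatment study would have called Possibly. The two cut-points then agree at that boundary.
- Likely takes in some of it. The cut-points differ in part.
- Likely takes in none of it. The cut-points differ by a whole category.

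The documents do not choose among these. Nor do they exclude that the treatment study defined Possibly more strictly than its name suggests. Both direction and size therefore stay open.

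**4. Whether imported events reach the related rows**

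SAP 10.6 gives imported events both a relatedness rule and a counting period, which would serve little purpose if they were never summarised. SAP 11.7.1.1 and 11.7.1.2 do not exclude them. Pooling is the natural reading, though it is not stated outright.

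**5. What would move in a table**

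The rows count subjects as a percentage of the FAS. A subject's status depends on the Possibly rule only if that subject's sole related event is an imported one rated Possibly. With k such subjects in a cohort of n, including Possibly raises the row by 100 × k/n percentage points. Neither k nor n is given: SAP 4.2 marks sample size as not applicable, and SAP 10.2 names three cohorts without sizes. If k = 0, the effect is zero.

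**The case against.** The strongest reply is that the SAP has handled this openly. It names both sources, gives each its own rule, and says the relationship is flagged separately. Related AEs of interest also have their own listing. Counting Possibly as related is the cautious choice for safety. Part of this stands: the present rule should not be replaced by a narrower one in the main row. But the sentence on flagging sits in a section about dataset flags. It does not say that the rows in SAP 11.7 are separated. Nor does the SAP say whether the listing will show an imported event's original category.

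A second reply is that the two cut-points may coincide, since Likely is itself worded in terms of a reasonable possibility. That also stands. A reader might infer from the category names that imported events face a lower threshold. The requirement in Likely that an alternative cause be unlikely makes this plausible, but without the treatment study's definition it cannot be established.

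A reader might go further and infer that relatedness will appear to fall over time purely because the scale changes. The documents do not support that:
- No table described in SAP section 11 shows related AEs by period, and the index of tables is redacted.
- The periods after Screening share one scale, so a change of scale could act only at the step from the treatment study.
- Only continuing events are imported, so the earlier period is a selected subset and not a sound baseline on any scale.
- A trend in relatedness is not an objective or endpoint.

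**Conclusion.** The point holds in a limited form. One related label rests on two category sets with no mapping, and the described AE and SAE summaries do not separate the sources. The related rows can therefore combine cut-points that may differ. This rests on one assumption: that imported events enter those rows, which SAP 10.6 implies but SAP 11.7 does not state.

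No numerical size can be given. Any figure for a change in the related share would need assumed proportions of events in each category, and a share of events is not what the planned tables report. The number of events involved is probably small because of the import rule. The case for change is that a primary-endpoint component should have one stated meaning per row, and that this costs almost nothing to achieve. It is a cheap improvement, not a threat to the study's conclusions.

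**What to change.** Amend SAP 10.6, 11.7.1.1 and 11.7.1.2 before database lock:

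- Report related AEs and related SAEs in separate rows for imported events and for events with onset in ADVM-043-03.
- Within the imported rows, show Possibly on its own line.
- Give the original causality category for every imported event in the listings.
- State in section 11.7 how imported events enter each summary, and what the separate flagging in 10.6 is meant to achieve.
- If a pooled row is kept, retain the SAP's current rule, footnote the two scales, and add a sensitivity count without Possibly. That count should not replace the main row. It sets Probably beside Likely, an equivalence the documents do not establish, and it drops events the SAP now treats as related.

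The cost is SAP wording and a few extra table rows, some of which may be nearly empty. No new data are needed.

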6.4 Assessment of Severity

The severity or intensity of an AE refers to the extent to which an AE affects the subject's daily activities. The intensity of the AE will be rated according to the Common Terminology Criteria for Adverse Events (CTCAE) (National Cancer Institute 2017):

- Grade 1: Mild; asymptomatic or mild symptoms; clinical or diagnostic observations only; intervention not indicated.
- Grade 2: Moderate; minimal, local, or noninvasive intervention indicated; limiting age-appropriate instrumental activity of daily living (preparing meals, shopping for groceries or clothes, using the telephone, managing money).
- Grade 3: Severe or medically significant but not immediately life-threatening; hospitalization or prolongation of hospitalization indicated; disabling; limiting self-care activity of daily living (bathing, dressing, and undressing, feeding self, using the toilet, taking medications, and not bedridden).
- Grade 4: Life-threatening consequences; urgent intervention indicated.
- Grade 5: Death related to AE.

Changes in the severity of an AE should be documented to allow an assessment of the duration of the event at each level of severity. AEs characterized as intermittent do not require documentation of onset and duration of each episode.

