8.1 Handling Missing/Incomplete Data

Missing data will not be imputed.

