11.7.1.2 Summary of Adverse Events of Interest by SOC and PT

Number and percentage of subjects will be summarized by cohort, system organ class and preferred terms. Percentages will be based on FAS population. Events will be displayed in the descending order of frequency in “Total”.

The same will be repeated for ADVM-043 related AEs of interest, Serious AEs of interest, ADVM-043 related serious AEs.

Listings for ADVM-043 related AEs of interest, serious AEs of interest will be listed similar to Listing 16.2.7.1 with respective information.

Death due to AEs will also be listed separately.

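### SAP 8.1 rules out imputation without exception, yet SAP 10.6 puts ungraded AEs into the summary tables as Grade 3, including an ungraded fatal AE that Protocol 6.4 would place at Grade 5

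*SAP*

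**What the plan says.** SAP 8.1 consists of one sentence, "Missing data will not be imputed", with no exception and no cross-reference.

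The severity paragraph of SAP 10.6 contains two rules. The first deals with several grades for one event: "Subjects with the same AE of interest and different severities will be flagged for the most intense severity". Its worked example uses two observed grades, 1 and 3. The second deals with absent grades: "AEs that are missing severity will be presented in summary tables as" Grade 3 (severe). It makes no separate provision for an AE with a fatal outcome.

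Two planned outputs use these grades. SAP 11.7.1.1 counts subjects with AEs of grade 3 or higher and, in a separate row, "Fatal adverse events". In SAP 11.7.1.3, subjects in each system organ class, "preferred term, and intensity (Grade 1-5) will be summarized by severity". The text of that section names no category for a missing grade.

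Protocol 6.4 sets the scale and ends with "Grade 5: Death related to AE". Protocol 6.6 asks for the investigator's assessment of severity for each event and, as a separate item, its outcome.

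**The concern.** Placing a fixed grade where none was recorded is single-value substitution in the reported result, whatever it is called. SAP 8.1 tells the reader that this does not happen, and SAP 10.6 does it. Someone who relies on 8.1 would take every entry in the severity table as an investigator's grade.

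Severity is a named component of the study's only endpoint (SAP 7.1). If any AE is ungraded, its assigned grade falls exactly on the boundary of the grade 3 or higher row, so that row is the summary most exposed to the rule.

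The fatal case differs in kind. For a non-fatal AE, Grade 3 is a cautious guess at an unknown value. For a fatal AE, the protocol's own scale already fixes the grade, so the rule replaces a value that can be worked out with one that is wrong.

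**Working it through.** The documents state no sample size, cohort size or expected number of ungraded AEs, so there is no figure in the plan to reproduce. The check applies the rules as written.

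**Step 1: the two sections side by side.** 8.1 covers all missing data and allows no substitution. 10.6 covers missing AE severity and substitutes Grade 3 in the tables. Both cannot hold literally unless 8.1 names 10.6 as an exception, which it does not.

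**Step 2: an ungraded, non-fatal AE.** Assigned grade = 3. Since 3 ≥ 3, the subject enters the grade 3 or higher row. If the true grade was 1 or 2, the subject is there only because of the rule, unless another AE of grade 3 or higher puts the subject there anyway.

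**Step 3: an ungraded fatal AE.**
- Severity table under SAP 10.6: Grade 3.
- Protocol 6.4 scale: Grade 5. Difference: 5 − 3 = 2 grades too low.
- Grade 3 or higher row: 3 ≥ 3 and 5 ≥ 3, so the count is correct either way.
- Fatal row and death listing: the event is counted and listed, taking both to be built from the outcome field that Protocol 6.6 collects apart from severity.

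The report would therefore show one event as fatal in one table and as Grade 3 in another.

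**Step 4: one AE with an observed grade g and an ungraded entry.**

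| g | Maximum over observed grades, then the Grade 3 rule | Grade 3 rule first, then the maximum: max(g, 3) |
|---|---|---|
| 1 | 1 | 3 |
| 2 | 2 | 3 |
| 3 | 3 | 3 |
| 4 | 4 | 4 |
| 5 | 5 | 5 |

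The orders differ only for g = 1 and g = 2, and in both cases the difference crosses the grade 3 boundary. The natural reading of 10.6 is the middle column: an AE with an observed grade is not missing its severity. The table shows only why a confirming clause is worth adding.

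**Step 5: scale, with n assumed.** One subject who enters the grade 3 or higher row only through the rule moves the cohort percentage by 100/n points, where n is the number of FAS subjects in the cohort: 33.3 at n = 3, 16.7 at n = 6, 10.0 at n = 10 and 5.0 at n = 20. This is arithmetic for any one-subject change, not an estimate of the effect here.

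**The case against.** The strongest defence is that 8.1 is a general rule and 10.6 a specific, prespecified one. 10.6 speaks of how AEs are presented in tables, which suggests a display convention that leaves the recorded data untouched. SAP 8 lists all data recorded in the eCRF and 11.7.1.1 lists all AEs, so an assigned grade can be traced. The rule errs towards greater severity, and no test or error rate depends on it. Most of this stands, and it is why the point is minor. It does not remove the mismatch: the summary tables are what most readers use, and 8.1 still says without qualification that nothing is filled in.

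On the fatal case, the defence is that it is remote and contained. It needs a fatal AE of interest whose severity was left blank although Protocol 6.6 asks for it, and "Death due to AEs will also be listed separately". That also stands. What remains is a rule that, followed literally, gives a wrong entry and makes two tables disagree.

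A reader might infer more in three places.
- That assigned grades will go unmarked in the tables. The index of tables in SAP 13 refers to a redacted source, and footnotes usually sit in table shells, so the documents cannot show this.
- That 10.6 leaves the order of its two rules open, so that programmers would produce different tables. Protocol 6.4 does say "Changes in the severity of an AE should be documented to allow an assessment of the duration of the event", so one AE can carry several entries. But an entry that records a change in severity would normally carry a grade, and the natural reading of 10.6 already takes observed grades first.
- That deaths would be lost. They would not: only the severity grade would be wrong.

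**Conclusion.** The point holds and is minor. SAP 8.1 and 10.6 contradict each other as written. The Grade 3 rule can mix observed and assigned grades in two summaries of a named endpoint component, and it misplaces an ungraded fatal AE by two grades in the severity table.

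How often this would happen cannot be determined from the documents, and the answer may be never. The conclusion rests on the text of the rules, not on any assumed rate of missing grades. It assumes that 10.6 is applied literally to fatal AEs and that the redacted table shells contain no overriding instruction for them.

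A reader might go further and conclude that a Grade 3 convention is itself unsound or biases the safety result. The documents do not support that: a conservative convention is defensible once it is declared and its use can be counted.

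**What to change.** Before database lock, make three wording changes.

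1. **SAP 8.1:** name the severity rule in 10.6 as an exception, and footnote the number of assigned grades in each affected table (the 11.7.1.1 overview and the 11.7.1.3 severity table). Alternatively, drop the Grade 3 assignment and show ungraded AEs in a Missing row.
2. **SAP 10.6, fatal AEs:** state that an AE with a fatal outcome and no recorded grade is shown as Grade 5. Any grade the investigator did record stays unchanged. The exception in 8.1 should cover this assignment too, under either option in item 1.
3. **SAP 10.6, order:** confirm that the maximum is taken over observed grades, and that the Grade 3 rule (or the Missing row) applies only when no grade was recorded for that AE.

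The cost is a few sentences plus one footnote or one extra table row. No new data and no protocol change are needed, because severity and outcome are already collected under Protocol 6.6.
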